4.1.1 Facilitator Selection and Training

Intervention group facilitators will be local residents proximal to the target population. Study staff will recruit former IDUs or individuals who have experience with the target population. Facilitators must have a good understanding of participants' worldview and health beliefs. They must be able to fully understand the dimensions of family and interpersonal relationships, sex roles, drug use history and the openness with which sex and drug use are discussed in the selected study sites. A highly scripted, culturally specific intervention manual will be followed, based on the SHIELD manual. A four-day facilitator training on facilitation, group processes, ethical guidelines, social cognitive and social influence models of behavioral change will be held during the first three months of study preparation. As part of their training, the facilitators will be made aware of gender roles and norms in the specific site context and how these shape the sexual decision-making process. They will be given a variety of teaching materials on AIDS, drug use and practices, AIDS risk factors, safer sex practices and group counseling; and will also be provided with a referral list for services such as employment training, detoxification and rehabilitation programs and HIV counseling centers to refer study participants who may request or need additional professional help.

4.1.2 Booster Sessions

Within no more than 2 months (60 days) following their 6-month and 12-month follow-up target dates, index participants who were randomized to the treatment arm will meet in small groups with a maximum of 12 participants for a one to two hour booster session. Participants must complete the follow-up visit prior to attending the booster session. An index may not attend a booster session once the 60-day window closes. These booster sessions will afford the indexes additional opportunities to troubleshoot, share their outreach experiences and lessons learned, improve their outreach communication styles, and maintain their motivation to promote HIV prevention among network members and in the community. It will not be necessary for experimental group index participants to attend the booster sessions with the same group of participants with whom they attended their peer educator training; however, the same groups will be reformed for the booster sessions, whenever possible.

4.2 Enhanced Risk Reduction Counseling and HIV Testing Intervention

Indexes and network members in the study will be offered two enhanced counseling sessions in conjunction with HIV testing. Each counseling session will involve a 10-to 15-minute client-centered, interactive approach that focuses on: 1) increasing the participant's perception of personal risk, 2) supporting participant initiated protective behavioral changes, and 3) focusing on the pursuit of small, achievable steps toward reducing personal risks.

Every effort will be made to have participants see the same counselor for both their pre- and post-HIV test sessions at each HIV testing time point. The first counseling session will be offered directly prior to the phlebotomy for HIV antibody testing at study screening and at each followup visit for HIV testing. The second counseling session will be conducted in conjunction with the confidential disclosure to participants of their HIV test results. Counselors will receive intensive training from study coordinators and experts experienced with this approach before offering counseling to any study participants.

All counseling sessions and disclosure of test results will be offered in private rooms with only the counselor and the participant present, to ensure the maintenance of participant confidentiality. The following guidelines will be followed:

- No one but the participant will be notified of his/her HIV status in the post-test counseling session.
- It is solely the right and choice of the participant to disclose his/her HIV status to others, except as mandated by local reporting requirements.
- Counselors will discuss potential consequences of participant disclosure of serostatus during the post-test counseling session.
- Neither counselors nor any other member of the study staff will provide information about a participant without a written and signed request from the participant, except as required by local reporting laws. If a participant makes such a request, the desired information will only be directly released to him/her.

The two-session, HIV test and interactive risk reduction counseling will be modeled after the two-session, brief counseling arm offered in Project RESPECT, described below. This counseling model was selected as the HIV counseling and testing model for this study because it has been proven effective in increasing condom use and prevention of new STIs. Because it is

well documented, use of this model will help to standardize the delivery and quality of the counseling and testing offered throughout the study.

Project RESPECT was a multi-center, randomized, controlled trial of 5,758 heterosexual HIVuninfected participants who presented for STI examinations in five US public STI clinics.³¹ Participants were randomized to one of three individual face-to-face HIV/STI prevention counseling intervention arms: Arm 1 received a four session counseling intervention, involving four behavioral theory-based sessions; Arm 2 received a brief counseling intervention involving two sessions based on CDC's client-centered, interactive HIV prevention counseling model; and Arm 3 received didactic messages, involving two brief, information-only sessions.

In both the four-session enhanced and two-session brief counseling interventions, participants' self-reported 100% condom use was higher (p < .05) at three and six months post intervention, compared to participants who received didactic messages. In addition, 30% fewer participants had new STIs (p=.002) in both counseling interventions than did participants in the didactic message group.

The brief counseling approach utilized in Project RESPECT placed a strong emphasis on condom use as a means of HIV risk reduction. The approach used in this study will be modified to also feature counseling about risk reduction relevant to injection drug use. This will include counseling about the use of clean needles and the importance of not sharing needles and other injection equipment.

5.0 STUDY PROCEDURES

An overview of the visit procedures schedule is provided in Appendix II. Detailed instruments to guide standard study procedures across sites will be provided in the Study Specific Procedures (SSP) Manual. Presented below is additional detail on visit-specific study procedures for index and network participants.

5.1 Screening (-60 to -1 Days)

Determination of the final eligibility of networks will take up to 60 days. Written informed consent for screening will be obtained before any screening procedures are initiated and study consent will be obtained prior to initiation of any study procedures. As noted in the study design and randomization schema on page 3 and in Section 3.4, for participants who do not meet the study eligibility criteria, the screening process will be discontinued when ineligibility is determined, however HIV counseling and testing will be available to all persons who present for study screening.

5.1.1 Screening of Index Participants

At the initial screening visit, prospective index participants will undergo the following:

- Written informed consent for screening
- Collection of locator information
- Eligibility screening survey
- Baseline HIV risk behavior survey (prior to counseling)
- HIV pre-test and risk reduction counseling
- HIV testing

For non-rapid HIV tests, prospective index participants will be asked to return in approximately one week for their second counseling session and their HIV test results and to undergo further eligibility screening. If the site is using rapid HIV testing, the potential participant will be asked to wait for the results. Regardless of which test the sites use for screening, the procedures for post-test counseling are the same. Those who test HIV-positive are not eligible for further screening and will receive post-test counseling and referrals as described in Section 8.4.1. Those who test HIV-negative and are otherwise eligible for further screening will undergo the following:

- Confirm identity and update locator information
- Written informed consent for the study
- HIV test results and post-test counseling
- Collection of identifying information for network members
- Baseline questionnaire (to assess network norms and frequency and duration of contact and types of discussions with network members. Note: These assessments can be completed at any visit prior to randomization.)

As part of the network member recruitment process, prospective indexes will be provided with individual cards marked with an identification number, and participants will be asked to give the cards to their relevant network members identified to the study staff.

5.1.2 Screening of Network Members

Since randomization and enrollment of a network must occur within 60 days of the first screened participant's pre-test visit, an individual who was provided with an identification card by an index participant and identified as a member of his/her HIV risk network must come into the local study site and complete all study screening procedures before the end of this 60 day period in order for the network to be eligible.

Screening of network members is expected to take place over one (for rapid tests) or more visits. During the pre-test visit, prospective network members will undergo the following:

- Written informed consent for the study
- Eligibility screening survey
- Baseline HIV risk behavior survey (prior to counseling)
- HIV pre-test and risk reduction counseling
- HIV testing

During the post-test visit (which may occur the same day if using the rapid tests), network members will receive their HIV test results, post test counseling, and appropriate referrals. In addition, network members will be administered baseline questionnaires to assess network norms and frequency and duration of contact and types of discussions with their index members. Note: These assessments can be completed at any visit prior to randomization.

5.2 Study Enrollment/Randomization of Index and Network Members (Day 0)

An eligible network consists of an index and one or more network members who have presented for screening, been found to be eligible, and provided study consent. Screening and eligibility procedures for all index and network members must be completed within 60 days of the randomization date. Eligible index participants will be randomized along with their network

members to either the experimental or control arm. Those index members randomized to the experimental arm will be provided instructions about when their first peer-education training session is to take place; this will be within approximately one week of randomization. Network members will be contacted to inform them of their eligibility/enrollment status.

5.3 Follow-up Visits

Follow-up visits are scheduled to take place every six months from enrollment/randomization until the study end date; however, they may take place any time within the period extending from 14 days prior to the target date to 30 days after the target date. Visits that do not take place during this period are treated as interim visits (see Section 5.5). Post-test counseling visits will occur either the same day (for rapid tests) or in approximately 7 to 14 days (for non-rapid tests) after HIV testing. For the purposes of scheduling follow-up visits, a single "Day 0" enrollment/randomization will be assigned to all network members according to the randomization date of their respective index.

Participants will undergo the following:

- Identity confirmation
- Update locator information
- Risk Behavior Survey Note: The risk survey must be administered prior to the delivery of HIV counseling, by a staff member who has not previously provided HIV counseling to the participant and is blinded to participant' study arm assignment.
- Enhanced risk reduction counseling
- HIV testing according to Appendix I
- Follow-up questionnaire to assess the intensity of the intervention delivery by the index in indexes themselves and network members (duration of contact and types of discussions), intervention contamination in the control arm, and perceived network norms (every 12 months)
- Social harms assessment
- Reiteration of study site contact information and instructions to contact the site for additional information about the study and/or HIV counseling, if needed, prior to the follow-up HIV post-test counseling visit.

Note: Network members identified as HIV-infected at baseline and index participants and network members identified as HIV-infected after enrollment will remain in follow-up and undergo all scheduled assessments except HIV testing.

5.3.1 Follow-up Post-test Visits

Regardless of HIV test results, participants who undergo HIV testing will complete a followup, post-test visit approximately 7 to 14 days after testing if using non-rapid testing or the same day if using rapid testing. During this visit, (at a minimum) their HIV test results will be disclosed and HIV post-test counseling and appropriate referrals will be provided.

5.4 Locator contacts

Locator contacts are scheduled to take place in between participant's scheduled six-month followup visits; therefore, all participants will be in contact with study staff quarterly throughout follow-up. The contacts in between the scheduled follow-up visits may take place via any modality that the study site deems appropriate for the local study population. Locator information, which includes the address and telephone number of each participant, and contact information for friends and family members will be updated.

5.5 Interim Visits

Interim contacts and visits may be conducted at participant request at any time during the study. Locator information will be updated and interim HIV counseling and testing will be provided as needed in response to participant reports of potential exposure to HIV. All interim contacts and visits, and the results of all interim HIV tests will be documented in participants' study records and on applicable case report forms.

5.6 Study Endpoint Assessment for Participants Who Withdraw

Participants who withdraw from the study (see Section 3.7) will be asked to participate in an endof-study assessment of their HIV status. In the last six months of the study, site staff will initiate contact with these participants who withdrew from the study, and they will be asked to undergo HIV counseling and testing only.

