3.7 Participant Withdrawal

Participants may withdraw from the study for any reason at any time. The investigator also may withdraw participants from the study in order to protect their safety and/or if they are unwilling or unable to comply with required study procedures. See Section 5.6 for assessments to be performed if possible for participants who withdraw. Participants also may be withdrawn if the sponsor or regulatory authorities terminate the study prior to its planned end date. Indexes who do not complete the peer education training will continue in the study and will complete all follow-up visits as scheduled, as will their network members.

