6.1 Monitoring of Social Harms

In order to prevent against adverse social events, "social harms" will be monitored closely throughout the study. At each follow-up visit, a series of structured questions will be used to probe for interpersonal, legal, housing and healthcare problems that have occurred as a result of study participation. All subjects will also be reminded of the importance of reporting problems to study staff between regularly scheduled visits and instructed on how to contact study staff should problems occur during intervals between visits. When problems are identified, additional data regarding the severity and resolution will be described and recorded on a separate reporting form and will include a description of actions taken by the participant, the site staff, and others to resolve or respond to the problem. The nature and frequency of these social impact reports will be monitored by the protocol team as they occur. In addition, these data will be routinely reviewed by the DAIDS Prevention Data and Safety Monitoring Board (DSMB).

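### No social harms questions are planned at or after withdrawal, so harm after a leaver's last visit is captured only if the participant reports it or staff notice it

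*Protocol*

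**What the plan says.** Section 3.7 lets participants leave at any time for any reason and lets the investigator withdraw them. For what to do then, it gives one pointer: "See Section 5.6 for assessments to be performed if possible for participants who withdraw".

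Section 5.6 concerns HIV status at the end of the study. On timing: "In the last six months of the study, site staff will initiate contact with these participants who withdrew from the study". On content: "they will be asked to undergo HIV counseling and testing only".

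Section 6.1 sets out how social harm is found and recorded:
- Active: "At each follow-up visit, a series of structured questions will be used to probe for interpersonal, legal, housing and healthcare problems".
- Passive: "All subjects will also be reminded of the importance of reporting problems to study staff between regularly scheduled visits".
- Recording: "When problems are identified, additional data regarding the severity and resolution will be described and recorded on a separate reporting form". The protocol team monitors these reports as they come in, and the DSMB reviews them routinely.

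Section 5.3 and the visit table in Appendix II place the social harms assessment at the six-monthly follow-up visits. Neither lists a withdrawal visit.

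**The concern.** Harm is actively sought in those who stay and passively received from those who leave. A participant harmed after the last attended visit, who leaves because of it, meets no structured question about it at any later point.

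Social harm is the main safety information in this trial. Section 6.0 expects no biological adverse events from a behavioral intervention and names discrimination and violence as possible consequences of taking part. If leaving is related to harm, counts based mainly on attended visits will be too low. If such leaving were also more common in one arm, the comparison before the DSMB would be distorted. The protocol gives a reason to ask, since only experimental-arm indexes are trained to do outreach, but it gives no evidence that this causes harm or withdrawal.

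**Working it through.** The point concerns a data-collection rule, so the check is mainly a reading of each route by which harm could be recorded in someone who withdraws.

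| Route | Where | Covers harm after the last attended visit? |
|---|---|---|
| Structured questions at six-monthly visits | 5.3, 6.1, Appendix II | No; covers only the time up to the last visit attended |
| Participant reports between visits | 6.1 | Only if the participant volunteers it |
| Locator contacts between visits | 5.4 | Not by design; the listed content is contact details |
| Interim visits | 5.5 | At the participant's request; locator update and HIV counseling and testing are listed, harm questions are not |
| Separate reporting form | 6.1 | Yes, but only once a problem has been identified |
| Contact with withdrawn participants | 5.6 | No; HIV counseling and testing only |

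No row provides active questioning after the last attended visit.

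**Timing of the 5.6 contact.** Section 2.3 gives about 48 months in total, so the last six months are months 42 to 48. Someone enrolled at the start who withdraws at month 6 would be contacted 42 − 6 = 36 to 48 − 6 = 42 months later.

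**Scale.** The protocol states no figure for withdrawal. The nearest input is loss to follow-up of 10% per year from any cause, with projected enrollment of 2,610 (both Section 7.3.1). The proportion lost by t years is 1 − 0.9^t.
- 18 months: 1 − 0.9^1.5 = 0.146; 0.146 × 2,610 ≈ 382.
- 30 months: 1 − 0.9^2.5 = 0.232; 0.232 × 2,610 ≈ 604.
- One six-month interval between structured assessments: 1 − 0.9^0.5 = 0.051, about 5% of those still in follow-up.

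The first two figures bound withdrawals from above if the planned loss rate holds. They are not estimates of withdrawals, and still less of missed harms.

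**The case against.** The best defense is that Section 6.1 already supplies several routes. Participants are questioned at every visit they attend, told to report problems in between and told how. Any problem identified goes on a form that is not tied to a visit. Section 5.4 keeps staff in contact quarterly. This stands, and it limits the gap to harm after the last visit that is neither reported nor noticed. A reader might infer that social harm in leavers is never recorded; these routes show otherwise.

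A reader might also point to Section 3.7, where "The investigator also may withdraw participants from the study in order to protect their safety", and infer that even harm behind a safety withdrawal is lost. The text does not support that. If an investigator withdraws someone because of a known social harm, the problem has been identified and Section 6.1 already calls for the form.

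Nor is there a strict contradiction with Section 6.1, which says harms "will be monitored closely throughout the study". That can fairly be read as applying to people in follow-up. In Section 5.6, the restriction serves to ask little of people who chose to leave, and it does not forbid staff to record a harm mentioned at the contact.

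Finally, the study procedures manual and case report forms are not shown and may already collect reasons for withdrawal. That stands, so the absence of such an item is not claimed here. It does not answer the main point, because Section 5.6 itself fixes what withdrawn participants are asked.

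**Conclusion.** The point holds in a limited form. By stated rule, no structured social harms assessment takes place at or after withdrawal, and an analysis plan cannot recover answers that were never sought. Harm counts may therefore be too low for the time after the last attended visit.

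The size is unknown. It depends on how many of those lost are withdrawals, how often harm arises after the last visit, and how much of it is volunteered or noticed; the protocol gives none of these. A difference by arm is possible but cannot be shown from the text, and neither can the inference that those who withdraw are the people most likely to have been harmed. This is a cheap improvement to safety ascertainment, not a threat to the primary HIV comparison.

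**What to change.** In Section 5.6, replace the restriction to HIV counseling and testing with HIV counseling and testing followed by the existing Section 6.1 social harms questions. Keep the questions voluntary and ask them after the HIV test, so that refusing them does not cost the primary endpoint result.

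In Sections 3.7 and 5.6, add that the same questions are offered at the time of withdrawal when the participant is in contact with staff. This is the more useful occasion: recall is fresh, and the answers reach the DSMB while the study is running. Include the results from both occasions, by arm, in the DSMB social harms review.

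The cost is a wording change and reuse of an existing set of questions. The end-of-study contact is already planned, and the offer at withdrawal needs no new visit if limited to people already in contact. The downsides are slightly more burden on people who chose to leave, some refusals, and weaker recall at the late contact.
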